#### **Procedure**

Potential participants will be identified through their initial assessment upon referral to the Chronic Pain Service. Those who are deemed to be suitable for a Pain Management Programme (e.g. capacity, motivation) will be offered an introductory group session, followed by invitation to an upcoming 11-week group. Information sheets and consent forms will be given out at the start of the group (week 1), to be completed and returned the following week. The information sheets will contain details about the purpose of the research, expectations of the participant in taking part and further information about consent, potential benefits, confidentiality and details of the researchers. Participants will be given time to consider the information and direct questions to the clinical team, to go home and consider the information privately, and also given the opportunity to phone the service and ask further questions if desired. Those who can provide written informed consent will complete pre-group measures at the start of week 1. Mid-group measures will be completed at the end of week 5 and post-group measures will be completed at the end of week 11. (See section 6.4 for details of outcome measures.) The clinical team will be available if participants require support to complete the measures (e.g. literacy issues). The data for participants who do not complete the group will not be used in the final analysis.

### Intervention

All groups will follow the same 11-week, structured timetable, using Compassion-Focused Therapy. As there are no current guidelines for using CFT in chronic pain, exercises have been adapted from 'Compassion Focused Therapy for Dummies' (Welford, 2016), incorporating the key elements of CFT (Gilbert, 2009).

#### **Data Collection**

Demographic information routinely collected by the service will be used for descriptive statistics (gender, age, area of residence, pain diagnoses and other relevant physical health conditions, duration of pain, employment status and recent pain-related contact with healthcare services).

The following self-report measures will be completed by participants at the beginning of week 1 (start) and at the end of week 11 (end). Questionnaires denoted with '\*' will be completed by participants at these time intervals and, additionally, at week 5 (mid-point).

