# Design

This study will follow a within-group (non-randomised) effectiveness-implementation design (Curran, 2012). Five self-report measures will be completed by participants at three specified time periods (pre-, mid- and post-group; see *Procedure* below).

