# Sample Size

Fritz and MacKinnon (2007) propose guidelines for recommended sample sizes in order to detect mediation effects with .8 power. These guidelines are informed by existing literature in the field. There is less robust research on self-compassion and chronic pain, therefore, this calculation is based on research in psychological flexibility and chronic pain.

McCracken and Gutierrez-Martinez (2011) conducted correlational analyses on the processes of psychological flexibility following a group intervention based on ACT. These processes included acceptance of pain, mindfulness, psychological acceptance and values-based action (r values between 0.33 and 0.55). These positive correlations indicate that the group intervention was related to higher levels of psychological flexibility.

A review by Hayes and others (2006) identified several studies that reported correlational effect sizes between acceptance, and depression/anxiety/daily functioning related to chronic pain (r = -0.58/-0.66/0.47 respectively). These negative correlations illustrate that higher levels of psychological flexibility were related to better outcomes.

Based on these correlational effect sizes, Fritz and MacKinnon's guidelines suggest that a sample size of 53-71 is required.

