## **Analysis**

The analysis will focus on the proposed mediating factors (self-compassion and psychological flexibility) and how they explain the outcome of the CFT-incorporated group intervention. In order to study the processes of change, this study will measure change in mediators and outcomes over the course of the group.

In a mediation model, the effect of the independent variable (IV; CFT group) on a dependent variable (DV; outcome/change in symptoms) is conveyed through a third mediating variable. In order to be a mediator, a variable must change during the intervention, be associated with the intervention, and have an impact on the outcome.

In this study, it is hypothesised that self-compassion and/or psychological flexibility are the mediating variables that explain the influence of the group intervention on eventual outcome, i.e. the overall change in symptoms at the end of the group. Linear regression and nonparametric bias-corrected bootstrap, which corrects for skew in the data, will be applied to the data using SPSS, using the PROCESS macro. An effect of mediation will be indicated if the confidence interval does not contain zero.

Missing data will be handled using either the maximum likelihood or multiple imputation method, as recommended in literature.

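### The mediator-change to outcome-change slope carries no baseline adjustment, so in this single-arm study a baseline factor that drives both changes can be read as mediation

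*Combined protocol and SAP*

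**What the plan says.** The Design section states: "This study will follow a within-group (non-randomised) effectiveness-implementation design". Every participant analysed attends the CFT programme, and there is no comparator.

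The Data Collection section says "Demographic information routinely collected by the service will be used for descriptive statistics". The list that follows includes age and ends with "duration of pain, employment status and recent pain-related contact with healthcare services". The text available states no other use for these variables.

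The Analysis section works with change: "In order to study the processes of change, this study will measure change in mediators and outcomes over the course of the group". The method is given as "Linear regression and nonparametric bias-corrected bootstrap, which corrects for skew in the data, will be applied to the data using SPSS", run through the PROCESS macro. No covariate is named, no adjustment for the baseline mediator or outcome score, and no sensitivity analysis for confounding. The decision rule is: "An effect of mediation will be indicated if the confidence interval does not contain zero". The confidence level is not stated.

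The questionnaires, including BPI-SF pain severity, are completed at the start of week 1. They are described separately from the routine variables, and nothing confines them to description.

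**The concern.** With everyone in the same intervention, the only between-person evidence on mediation is whether people whose mediator changed more also improved more. Mediator change is not randomised. If people with, say, shorter pain duration or lower baseline severity tend both to gain self-compassion and to improve in mood, the regression shows a slope even when the mediator does nothing. The decision rule would then report mediation.

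A larger sample does not reduce this bias. It narrows the interval around a biased slope, so zero is excluded more often. The secondary question, which of the two mediators predicts change better, is exposed in the same way.

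Analysing change removes stable differences in level between people. It does not remove factors that predict change itself. Baseline scores are natural candidates, because people who start at an extreme tend to move back towards the average.

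**Working it through.** **Inputs from the documents.** Sample size 53-71, with "recommended sample sizes in order to detect mediation effects with .8 power" as the aim. Correlations in the Sample Size section: .33 to .55 for psychological-flexibility processes after a group intervention (the a-path); absolute values .58, .66 and .47 for acceptance with depression, anxiety and daily functioning (the b-path). No covariate allowance.

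**Assumptions.** Two-sided 5% level (95% interval). One omitted baseline factor C with correlation rho to both mediator change M and outcome change Y, over the range .2 to .5. The documents give no value for rho.

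**The plan's sample size.** Take Fisher-z power for the a-path times Fisher-z power for the b-path and require at least .80. The weakest documented pair (.33, .47) needs N = 72, close to the plan's 71. All documented pairs span 26 to 72. The lower figure, 53, cannot be re-derived exactly, because the guideline cell used is not given. These sizes rest on unadjusted correlations.

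**Spurious slope.** Let M = rho·C + e1 and Y = rho·C + e2, all standardised, with e1 and e2 independent, so that the true slope is zero. Then cov(M, Y) = rho², which is also the unadjusted standardised slope: .04, .09, .16 and .25 for rho = .2, .3, .4 and .5.

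**False-positive rate of the slope test.** With z = atanh(rho²)·√(n − 3), the rate is Φ(z − 1.96) + Φ(−z − 1.96). For rho = .4 and n = 53: atanh(.16) = .1614, times √50 = 7.071, gives z = 1.141 and a rate of .207.

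| rho | formula, n = 53 / 71 | simulated t-test, n = 53 / 71 | simulated, C adjusted for |
|---|---|---|---|
| .2 | 5.9% / 6.3% | about 6% / 7% | about 5% |
| .3 | 9.8% / 11.5% | about 10% / 12% | about 5% |
| .4 | 20.7% / 26.5% | about 20% / 26% | about 5% |
| .5 | 43.9% / 55.8% | about 44% / 56% | about 5% |

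**The planned bootstrap.** Simulating the bias-corrected interval for the indirect effect requires an independent variable that varies, which this study lacks, and an assumed a-path. With a = .55, false mediation at n = 53/71 was 11/9%, 14/15%, 29/34% and 51/61% for rho = .2 to .5, against 9/8% with no confounder. Another set of runs at rho = .4 gave 22/30% with a = .33 and 32/43% with a = .55. These rates are mostly higher than the slope test's and move with an input the documents do not fix, so I rest the size on the slope test.

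**What confounding would not do.** A single factor accounts for an observed slope r completely only if rho = √r: .69 for r = .47, .76 for .58, .81 for .66. The adjusted slope is (r − rho²)/(1 − rho²). For r = .47 it is .418, .369 and .293 at rho = .3, .4 and .5.

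**Cost in precision.** Five added terms in an outcome model with residual degrees of freedom n − 3 (intercept and two predictors) widen the interval by √(df0/df1) times the ratio of t quantiles.
- n = 53: √(50/45) × 2.0141/2.0086 = 1.057.
- n = 71: √(68/63) × 1.9983/1.9955 = 1.040.

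Both are before any gain from explained outcome variance.

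**The case against.** The best reply is that the size rests on an assumed rho, and that nothing in the documents shows age or pain duration to be correlated .3 to .5 with change in both variables. That stands. At rho = .2 the inflation is a point or two, and a moderate confounder would not erase slopes as large as those cited in the Sample Size section.

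A reader might infer that the plan forbids adjustment. It does not. The descriptive sentence never says only, and of the five proposed covariates it covers just age and pain duration. Baseline BPI-SF severity and the baseline mediator and outcome scores are study measures with no such restriction. The gap is that no adjustment is specified, which leaves it absent or open to choice after the data are seen.

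A reader might also infer that covariates would make the mediation claim sound. They would not. The independent variable is the same for everyone, so its path to the mediator cannot be estimated between people. Factors nobody measured stay in the slope, and the return to about 5% holds only if the confounder is measured well and is on the list.

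Nor is adjustment free. It uses degrees of freedom, and the slope may shrink once shared causes are removed. In a heavier case, with seven degrees of freedom spent, the weakest documented pair needs N = 78, 86 or 110 at rho = .3, .4 or .5, against 72 unadjusted.

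**Conclusion.** The concern holds in a limited form. The plan states only a descriptive use for age and pain duration and names no baseline adjustment. Its mediation rule is therefore applied to an unadjusted association between two changes in a single arm.

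If one omitted factor relates equally to both changes and there is no true slope, the inflation over a nominal 5% is negligible at rho = .2, modest at .3 and material from .4 upward. The direction does not depend on the bootstrap, since an ordinary slope test shows it too. The size depends wholly on rho, which is assumed. The documents do not show that any named covariate is a confounder, and they do not support saying that confounding would account for the whole of an observed slope.

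The plan should be changed, because the data are already being collected and the change removes a bias that recruiting more people cannot.

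**What to change.** In the Analysis section, prespecify that each outcome regression adjusts for the baseline mediator score, the baseline score of that outcome, baseline BPI-SF pain severity, age and pain duration. Fix the list before data are seen, and report the unadjusted model as a sensitivity analysis. In the Data Collection section, add that age and pain duration are also used as covariates. Word conclusions as association between mediator change and outcome change.

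No new data are needed. The price is the 5.7% (n = 53) or 4.0% (n = 71) wider interval shown above. If both mediators enter one model, the second baseline mediator score makes six terms, and the widening is about 7.0% and 4.9%. Part of this may be recovered if the covariates explain outcome variance. The 53-71 target makes no allowance for covariates, so it should be rechecked against the adjusted model.

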# **Anxiety and Depression\***

The Hospital Anxiety and Depression Scale (HADS) (Zigmond & Snaith, 1983) is a 14-item measure of the symptoms of anxiety (7 items) and depression (7 items) in individuals with physical health issues. Each of the items are scored from 0 to 3, where a higher score depicts greater frequency or intensity of the described symptom over the last week (e.g. "I get sudden feelings of panic" and "I have lost interest in my appearance"). Anxiety and depression are rated separately, each allowing for a minimum score of 0 or a maximum score of 21. Bjelland et al. (2002) reviewed 747 papers using the HADS and demonstrated a two-factor structure (i.e. anxiety and depression), with a high level of internal consistency for both the anxiety (Cronbach's alpha = .83) and depression (Cronbach's alpha = .82) subscales. Michopoulos et al. (2008) reported a high test-retest reliability of .94 over a 20-day period.

# Mental Wellbeing\*

The shortened version of the Warwick-Edinburgh Mental Wellbeing Scale (Taggart et al., 2015) (SWEMWBS; Stewart-Brown et al., 2009) is a 7-item measure reporting on subjective positive mental wellbeing and psychological functioning over the last two weeks. It aims to cover a broad range of positive mental health concepts (e.g. "I've been feeling confident" and "I've been feeling close to other people") but does not include spirituality or socioeconomic factors. Each of the items on the measure require a response on a Likert scale, from 1 (none of the time) to 5 (all of the time). This yields a minimum score of 7 and a maximum score of 35 (higher score indicating greater well-being). The SWEMWBS has a test-retest reliability of .83 and demonstrates stability after one week (Stewart-Brown et al., 2009).

## Pain

The Brief Pain Inventory (short form, BPI-SF; Cleeland & Ryan, 1994) is a 9-item measure designed to capture two aspects of pain: pain interference (with daily living) and pain severity. These two distinct dimensions have been confirmed through factor analysis. Responses to items on this measure range from 0 (does not interfere) to 10 (completely interferes) on the pain interference subscale and 0 (no pain) to 10 (pain as bad as you can imagine) on the pain severity subscale. The BPI-SF demonstrates stable test-retest reliability and high internal consistency, with Cronbach's alpha ranging from .80 to .92 (Cleeland, 2009). The Initiative on Methods, Measurement, and Pain Assessment in Clinical Trials (IMMPACT; Dworkin et al., 2005) recommends that all chronic pain research should include outcomes in pain interference and pain severity.

## Self-Compassion\*

Self-Compassion Scale (short form, SCS-SF; Neff, 2003) is a 12-item measure designed to assess a person's kindness and understanding towards themselves during difficult times. The three elements of self-compassion as defined by Neff (2003) exist on a dichotomy: self-kindness vs. self-judgement; common humanity vs. isolation; and mindfulness vs. over-identification. Responses to these items are indicated on a Likert scale, ranging from 1

(almost never) to 5 (almost always). The SCS-SF has a strong correlation with the long form measure, and factor analysis has validated the six-factor model, in addition to the single higher-order factor of self-compassion (Raes et al., 2011). The SCS-SF shows high internal consistency (Cronbach's alpha = .86; Raes et al., 2011) and good test-retest reliability over three weeks (scores of at least .8 across all subscales; Neff, 2003).

# Psychological Flexibility\*

Multi-Dimensional Psychological Flexibility Inventory (short form, MPFI-SF; Rolffs et al., 2016) is a 24-item measure assessing the flexibility of a person's response to negative internal experiences (e.g. thoughts and feelings). Psychological flexibility allows a person to carry these negative experiences whilst living their life in a meaningful, values-directed way. Twelve dimensions have been validated in the 6-factor model of psychological flexibility (Rolffs et al., 2016), the Hexaflex model (Hayes et al., 2011). Psychological flexibility encompasses present moment awareness, values, committed action, self-as-context, defusion and acceptance. Psychological inflexibility encompasses lack of contact with the present moment, lack of contact with values, inaction, self-as-content, fusion and experiential avoidance. Response to items range from 0 (never true) to 6 (always true) of items in the context of the last two weeks. The MPFI has been shown to have higher levels of internal consistency than other measures of psychological flexibility (Rolffs et al., 2016).

# Sample Size

Fritz and MacKinnon (2007) propose guidelines for recommended sample sizes in order to detect mediation effects with .8 power. These guidelines are informed by existing literature in the field. There is less robust research on self-compassion and chronic pain, therefore, this calculation is based on research in psychological flexibility and chronic pain.

McCracken and Gutierrez-Martinez (2011) conducted correlational analyses on the processes of psychological flexibility following a group intervention based on ACT. These processes included acceptance of pain, mindfulness, psychological acceptance and values-based action (r values between 0.33 and 0.55). These positive correlations indicate that the group intervention was related to higher levels of psychological flexibility.

A review by Hayes and others (2006) identified several studies that reported correlational effect sizes between acceptance, and depression/anxiety/daily functioning related to chronic pain (r = -0.58/-0.66/0.47 respectively). These negative correlations illustrate that higher levels of psychological flexibility were related to better outcomes.

Based on these correlational effect sizes, Fritz and MacKinnon's guidelines suggest that a sample size of 53-71 is required.

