## Methodology

# **Participants**

Participants will be adults with chronic pain who attend and complete the CFT-incorporated groups at the Lothian Chronic Pain Service / Pain Management Programme.

Inclusion Criteria	Exclusion Criteria
- Chronic Pain lasting a minimum of 3	- Active substance misuse
months	
 
Active suicidality
 

 
Fluency of English sufficient for
 
	- Terminal illness
participation in the group and	
 
Inability to provide informed
 

completion of questionnaires	consent (as defined by the Five
- Aged 18+ (no upper age limit)	Statutory Principles of the Mental

- Ability to provide informed consent	Capacity Act, Code of Practice,
as judged by the clinical team	2007)

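### The 53-71 sample size range misses its stated .8 power at the lower end for the smallest correlations quoted, and the .8 is not shown to apply to the planned single-group, two-mediator analysis

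*Combined protocol and SAP*

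**What the plan says.** The Sample Size section relies on a published guideline for "recommended sample sizes in order to detect mediation effects with .8 power". It quotes two sets of inputs, both from the psychological flexibility literature:

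- correlations for flexibility processes after a group intervention, "r values between 0.33 and 0.55";
- correlations of acceptance with depression, anxiety and daily functioning, "r = -0.58/-0.66/0.47 respectively".

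Of the first set it says: "These positive correlations indicate that the group intervention was related to higher levels of psychological flexibility". It then concludes that the "guidelines suggest that a sample size of 53-71 is required". It pairs no input with either end, and gives no alpha and no single target.

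Four other sections bear on the figure. Under Design, "This study will follow a within-group (non-randomised) effectiveness-implementation design". The Intervention section puts every group on one 11-week timetable. The Analysis section names the CFT group as the independent variable, self-compassion and/or psychological flexibility as mediators, and a bias-corrected bootstrap as the test. The Rationale describes the two mediators as strongly correlated. Only completers are analysed: participants are "adults with chronic pain who attend and complete the CFT-incorporated groups", and the Procedure adds: "The data for participants who do not complete the group will not be used in the final analysis".

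**The concern.** A range of effects naturally leads to a range of sample sizes. Here, however, the range is stated as what .8 power requires, so 53 reads as sufficient. If the true effects are the smallest that the plan quotes, 53 is not sufficient. The ends differ by 18 people (71 − 53), about a third of the smaller number, and the reader cannot tell which one completes recruitment.

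The second issue is which model the .8 belongs to. A power figure for a simple mediation chain needs an independent variable that differs between people. In this study everyone has the same exposure, and two related mediators are proposed. As written, the sentence reads as power for that analysis, and a null mediation result could then be given more weight than the design supports.

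**Working it through.** **Inputs from the documents.** Power .8; a path (to the mediator) .33 to .55; b path (mediator to outcome) .47, .58 or .66 in size; N of 53 to 71; bias-corrected bootstrap.

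**Assumptions, not in the documents.** 95% interval (two-sided .05), zero direct effect, one mediator, and a normally distributed independent variable X that varies between people.

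**Model.** The documents do not say whether the r values enter as correlations or as path slopes, so both were run:

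- correlations: M = aX + √(1−a²)·e₁, Y = bM + √(1−b²)·e₂;
- slopes with unit residual variance: M = aX + e₁, Y = bM + e₂.

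Mediation is declared when the interval for a·b excludes zero. The limits are the bootstrap quantiles at Φ(2z₀ ± 1.96), with z₀ = Φ⁻¹(share of resampled a·b below the estimate). Each cell uses 4,000 simulated studies and 1,000 resamples, so Monte Carlo error is at most about ±.015.

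**Reproducing 53-71.** It cannot be traced exactly, because no pairing is given. The upper end is consistent with the smallest inputs read as slopes: 71 gives .80 at .33/.47. The lower end does not match the N for .8 power at any pair of extreme inputs. An intermediate pair such as slopes of .39 and .59 (assumed) gives .81 at 53.

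**Power: correlations / slopes**

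| a, b | N = 53 | N = 71 |
|---|---|---|
| .33, .47 | .72 / .66 | .84 / .80 |
| .33, .66 | .72 / .70 | .83 / .81 |
| .44, .47 | .89 / .83 | .96 / .94 |
| .55, .47 | .88 / .90 | .96 / .96 |
| .55, .66 | .99 / .97 | 1.00 / .99 |

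Repeat runs at .33/.47 gave .70 to .73 and .65 to .68 at 53, and .84 and .80 at 71. At .44/.57, roughly the middle of both ranges, 53 gives .93 as correlations and .85 to .88 as slopes.

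**Why a larger b does not rescue 53.** The a path alone is the limit. By Fisher z, power = Φ(atanh(.33)·√(N−3) − 1.96):

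- N = 53: Φ(0.343 × 7.071 − 1.96) = Φ(0.46) = .68;
- N = 71: Φ(0.343 × 8.246 − 1.96) = Φ(0.87) = .81.

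With b = .47, 53 reaches .8 once a is about .37 (correlations) or .41 (slopes). At .33/.47, the N for .8 is about 64 as correlations and about 71 as slopes.

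**Choice of test.** At .33/.47 the percentile bootstrap gives less: .62 to .64 or .57 to .58 at 53, and .79 to .80 or .73 to .74 at 71. The planned bias-corrected interval is the more favourable method.

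**Does the model match the study?**

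- The a path is estimated as cov(X, M)/var(X). If everyone receives the programme, var(X) = 0 and the path is undefined.
- The quoted process correlations are described as correlational analyses after a group. Nothing quoted makes them an effect of the group on a mediator.
- With two mediators fitted together, the variance of each b estimate is multiplied by 1/(1−r²), where r is their correlation given X, other things equal. The documents give no r, so no two-mediator power is computed.

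**What a single group can size directly.** By the one-sample t test, a mean mediator change is detectable with .8 power at 0.39 SD of the change scores for N = 53 and 0.34 SD for N = 71. This is not power for mediation.

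**The case against.** The strongest reply is that nothing has been miscalculated. Small effects pair with 71 and larger effects with 53, and testing 53 at the smallest effects crosses the pairing. Much of this stands. Mid-range inputs give 53 more than .8, and 71 gives about .80 or more at every pair tested. The source guideline is not in the documents, so misuse of it cannot be shown. A reader might infer that the whole range is underpowered, or that the plan gives no inputs. Neither is supported: the section states the power and two sets of correlations. What remains is that one range is offered as required for .8, with no statement that its lower end depends on larger effects.

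Nor does any text make 53 a target or stopping point, so an early stop at 53 is only a possibility that the wording leaves open.

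A further reply is that moving to 71 on the strength of a model that does not fit the study is inconsistent. This is fair, and it limits the fix: 71 can be justified only as a planning figure under a named simpler model. The constant independent variable belongs to the Analysis section, and no choice of N repairs it.

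**Conclusion.** The point holds in two limited parts.

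1. At the smallest correlations the plan quotes, the lower end of its range gives about .66 to .72 instead of .8, while the upper end gives about .80 to .84. This rests on two-sided .05, zero direct effect, one mediator and a varying, normal independent variable. The spread reflects two readings of the inputs that the documents do not decide between.
2. The .8 is not shown to be a property of the planned analysis, which has a constant independent variable and two mediators described as strongly correlated. This part follows from the text and needs no simulation.

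The missing pairing of inputs to 53 and 71 is, on its own, only missing detail. A reader might also infer that 71 secures .8 for the planned analysis. It does not, because the model behind that figure is not this study's model. Confidence is medium. The change should be made, since a stated operating characteristic is not supported as written.

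**What to change.** Replace the 53-71 sentence with:

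> The target is 71 participants who complete the group and are analysed. Path values of .33 (to the mediator) and .47 (mediator to outcome) are planning assumptions. With one mediator, an independent variable that varies between people, zero direct effect, a bias-corrected bootstrap and two-sided .05, 71 gives power of about .80 to .84; 53 would give about .66 to .72. No .8 power is claimed for the mediated effect in a single group or for both mediators fitted together.

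Reword the sentence that reads the process correlations as an effect of the group:

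> The lowest of these correlations, .33, is used as an assumed path value and is not an estimate of the effect of the group.

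Optionally add that 71 gives .8 power for a mean mediator change of 0.34 SD of the change scores (0.39 at 53), noting that this is not power for mediation. Add no two-mediator figure unless a mediator correlation is stated as an assumption. Resolve the constant independent variable in the Analysis section; this wording does not.

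Cost: text only if 71 was already intended, otherwise up to 18 more analysed completers, still within the plan's own range. The Recruitment section's 2-3 new groups a month of up to 15 give 30 to 45 places. If 30% to 50% of places yield an analysed completer (assumed; no rate is given), that is 30 × .3 = 9 to 45 × .5 = 22.5 a month, so 18 more take about one to two months. The downside is a less favourable stated power.
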